6.2. Exclusion Criteria

Participants are excluded from the study if any of the following criteria apply at **screening (Week -4)** and **at randomization (Day 1)**, unless otherwise specified:

CKD Related Criteria

1. **Kidney transplant:** Planned living-related or living-unrelated kidney transplant within 52 weeks after randomization (Day 1).

Anemia Related Criteria

2. **Ferritin:** ≤ 100 ng/mL (≤ 100 μ g/L), at screening.
3. **Transferrin saturation (TSAT):** $\leq 20\%$, at screening. If TSAT is 18 to 20%, then a retest using a new blood sample can be obtained within 7 days of the final laboratory report; the final retest value must be $>20\%$ to confirm eligibility.
4. **Aplasias:** History of bone marrow aplasia or pure red cell aplasia.
5. **Other causes of anemia:** Conditions, other than anemia of CKD, which can affect erythropoiesis. A partial list can be found in the Study Reference Manual (SRM).

Cardiovascular Disease

6. **MI or acute coronary syndrome** within 8 weeks prior to screening through to randomization (Day 1).
7. **Stroke or transient ischemic attack** within 8 weeks prior to screening through to randomization (Day 1).
8. **Heart failure (HF)**: Chronic Class IV HF, as defined by the New York Heart Association (NYHA) functional classification system.
9. **Current uncontrolled hypertension** as determined by the investigator that would contraindicate the use of rhEPO.
10. **Bazett's correction of QTc interval (QTcB)** at Day 1: QTcB >500 msec, or QTcB >530 msec in participants with bundle branch block. There is no QTc exclusion for participants with a predominantly ventricular paced rhythm.

Other Medical Conditions

11. **Liver Disease**: presence of any one of the following liver-related laboratory values or conditions, at screening, is exclusionary:

- Alanine transaminase (ALT) >2x upper limit of normal (ULN);
- Bilirubin >1.5x ULN; or

NOTE: Isolated bilirubin >1.5x ULN is acceptable if bilirubin is fractionated and direct bilirubin <35%.

- Current unstable liver or biliary disease per investigator assessment, generally defined by the presence of ascites, encephalopathy, coagulopathy, hypoalbuminaemia, esophageal or gastric varices, persistent jaundice, or cirrhosis.

NOTE: Stable chronic liver disease (including asymptomatic gallstones, chronic hepatitis B or C, or Gilbert's syndrome) are acceptable if participant otherwise meets entry criteria.

12. **Gastrointestinal (GI) bleeding**: Evidence of actively bleeding gastric, duodenal or esophageal ulcer disease OR clinically significant GI bleeding \leq 8 weeks prior to screening through to randomization (Day 1).
13. **Malignancy**: History of malignancy within 2 years prior to screening through to randomization (Day 1), currently receiving treatment for cancer, or complex kidney cyst (e.g., Bosniak Category IIF, III or IV) >3 cm.

Note: The only exception is localized squamous cell or basal cell carcinoma of the skin that has been definitively treated \geq 8 weeks prior to screening.

Prior/Concomitant Therapy

14. **Drugs and supplements**: Use of a strong inhibitor of CYP2C8 (e.g., gemfibrozil) or a strong inducer of CYP2C8 (e.g., rifampin/rifampicin).

Prior/Concurrent Clinical Study Experience

15. **Severe allergic reactions:** History of severe allergic or anaphylactic reactions or hypersensitivity to excipients in the investigational product (refer to daprodustat IB), or epoetin alfa (refer to product labeling).
16. **Other interventional study participation:** Use of another investigational agent within 30 days or within five half-lives of the investigational agent (whichever is longer) or currently participating in a study of an investigational device prior to screening through to randomization (Day 1).
17. **Prior treatment with daprodustat:** Any prior treatment with daprodustat for treatment duration of >30 days.

Other Exclusions

18. **Other Conditions:** Any other condition, clinical or laboratory abnormality, or examination finding that the investigator considers would put the participant at unacceptable risk, which may affect study compliance (e.g., intolerance to rhEPO) or prevent understanding of the aims or investigational procedures or possible consequences of the study.

6.3. Lifestyle Restrictions

There are no lifestyle restrictions required for this study. Any restrictions of concomitant medications and non-drug therapies are described in Section [7.7.2](#).

6.4. Screen Failures

Screen failures are defined as participants who consent to participate in the clinical study but are not subsequently randomized. A minimal set of screen failure information is required to ensure transparent reporting of screen failure participants to meet the Consolidated Standards of Reporting Trials (CONSORT) publishing requirements and to respond to queries from regulatory authorities. Minimal information includes demography, screen failure details, eligibility criteria, and any SAEs.

Participants who do not meet the criteria for participation in this study (i.e., screen failure) may be rescreened up to two additional times as soon as the investigator assesses they may meet eligibility criteria. Participants who are to be rescreened must sign a new informed consent form and will be assigned a new participant number. The association between the initial/prior screening participant number and the new participant number must be documented.

6.5. Participant Retention

- Participants will be educated on the importance of remaining in the study and attending scheduled study visits.
- Investigators should make every effort to keep participants in the study, including those participants who have permanently discontinued study treatment.

- Should a participant fail to attend the clinic for a required study visit, the site should attempt to contact the participant and re-schedule the missed visit as soon as possible. The site should also counsel the participant on the importance of maintaining the assigned visit schedule. In cases where the participant does not return for the rescheduled visit, or cannot be reached to reschedule the missed visit, the site should make every effort to regain contact with the participant. The investigator (if allowed by local regulations) should obtain the name and phone number of a relative or friend to assist in contacting the participant.

7. TREATMENTS

Study treatment is defined as the investigational treatment or marketed product (i.e., daprodustat, matching placebo tablets, epoetin alfa or saline) intended to be administered to a study participant according to the study protocol.

7.1. Treatments Administered

GSK will provide the following study treatments: daprodustat and matching placebo tablets and epoetin alfa. Saline will be obtained locally. Study treatments are described in [Table 3](#).

Table 3 Description of Study Treatments

Study Treatment Name:	Daprodustat	Matching Placebo Tablets	Epoetin alfa	Saline
Dosage formulation:	Round, biconvex, white, film-coated tablet	Round, biconvex, white, film-coated tablet	Single-dose, preservative-free vials	Saline for IV use vials or bags
Unit dose strengths/ Dosage levels:	
Unit dose strengths: 7 mm tablets: 2 and 4 mg 9 mm tablets: 6, 8 and 10 mg Dosage levels: 2, 4, 8, 12, 16, 20, 24, 32 and 48 mg Dosages of 12 mg and greater will be provided using multiples of available tablet strengths. Details are provided in Table 5.
	
7mm tablets to match 2 and 4 mg daprodustat tablets 9 mm tablets to match the 6, 8 and 10 mg daprodustat tablets Dosage details are provided in Table 5.
	
Unit vial strengths: 2000, 3000, 4000 and 10,000 Units/mL Dosage level details are provided in Table 6.
	
0.9% sodium chloride Saline for IV use will be obtained locally; vial or bag size will vary. Dosage details are provided in Table 6.

Route of Administration	Oral	Oral	Intravenous	Intravenous
Dosing instructions:	
Participants will be dispensed the prescribed number of tablets.
 
The dose will be administered on a dialysis day, and may be given before, during or after the dialysis session. Participant may take dose at home prior to PD sampling visit.
 
Participants will take tablets with water and can be taken without regard to food.
	
Participants will be dispensed the prescribed number of tablets.
 
The dose will be administered on a dialysis day, and may be given before, during or after the dialysis session. Participant may take dose at home prior to PD sampling visit.
 
Participants will take tablets with water and can be taken without regard to food.
	
Site staff will withdraw the prescribed dose from each single-use vial into a syringe.
 
Multiple vials may be required to achieve the prescribed dose.
 
The dose will be administered to the participant during the dialysis session.
	
Site staff will withdraw the prescribed dose into syringe(s).
 
The dose will be administered to the participant during the dialysis session.

Packaging and Labeling	
Tablets will be provided in white, opaque high density polyethylene (HDPE) bottles with child-resistant closures. Each bottle will be labeled as required per country requirement.
	
Tablets will be provided in white, opaque high density polyethylene (HDPE) bottles with child-resistant closures. Each bottle will be labeled as required per country requirement.
	
Epoetin alfa will be provided in single-use, preservative-free vials. Each vial will be labeled as required per country requirement.
	
Not applicable (Saline for IV use will be obtained locally.)

Manufacturer	GlaxoSmithKline	GlaxoSmithKline	Janssen	Not available (Saline for IV use will be obtained locally)

Participants will discontinue their therapy with rhEPO or its analogs prior to randomization so that the randomization date (Day 1) coincides, as closely as possible, with the date of next scheduled administration of rhEPO or analog. Examples of switching will be provided in the SRM.

All study treatments should be taken in the clinic, with the exception that the blinded study treatment tablets may be taken at home prior to the study visit at which PD samples will be collected (see Section 9.6). The site must ensure that the date and time the participant took each dose of study treatment is documented. Participants will be given diary cards to record the date and time of any study treatment tablets taken at home. Additional instructions can be found in the SRM.

7.2. Starting Dose and Dose Modification

Participants will be randomized to receive either daprodustat or epoetin alfa.

In order to maintain the treatment blind, each participant will be administered both tablets and IV injections, with one formulation containing active study treatment and the other formulation being an inactive treatment. Refer to Section 7.4 for additional information regarding blinding.

Participants who are randomized to the daprodustat arm will receive the required number of daprodustat tablets to achieve the prescribed dosage of daprodustat based upon the starting dose and dose adjustment algorithms (see Section 7.2.1), and the required number of syringes with saline for IV administration to achieve the prescribed inactive treatment (see Section 7.2.2.2).

Participants who are randomized to the epoetin alfa arm will receive the required number of vials of epoetin alfa to achieve the prescribed dosage of epoetin alfa based upon the starting dose and dose adjustment algorithms (see Section 7.2.2), and the required number of placebo tablets to achieve the prescribed inactive treatment (see Section 7.2.1.2).

The dose of both study treatments will be adjusted, based on the algorithm in Section 7.2.3, in order to maintain Hgb concentrations in the target range. Any required dose adjustments should be started on the day of the study visit at which the dose adjustment was prescribed. In circumstances where a new supply of study treatment (including a new dose) cannot be dispensed on the day of the study visit, the new supply of study treatment can be dispensed at the next dialysis session, and the prior study treatment should be continued unless on a dose interruption.

7.2.1. Participants Randomized to Daprodustat

Participants who are randomized to the daprodustat treatment arm will receive daprodustat tablets and saline IV. A starting dose will be assigned for daprodustat as described in Table 4. A starting dose will be assigned for saline, following the algorithm described for epoetin alfa in Section 7.2.2.1. Dose levels will be titrated for both the active and inactive study treatments, and new containers dispensed for each treatment with each change in dose.

7.2.1.1. Daprodustat Starting Dose

The starting dose of daprodustat will be assigned based on prior rhEPO or analog dose at randomization, Day 1 (Table 4).

Table 4 Daprodustat Starting Dose

[figure not shown]
RhEPO or Analog Dose at Randomization (Day 1)			Daprodustat Dose
Epoetins (including biosimilars) (U/week IV) ¹	Darbepoetin ($\mu\text{g}/4\text{week SC/IV}$) ²	Methoxy PEG-Epoetin beta ($\mu\text{g}/\text{month SC/IV}$) ^{3,4}	(mg, three-times weekly)
1500 to 2000	20 to 30	30 to 40	8
> 2000 to < 10000	>30 to 150	>40 to 180	12
$\geq 10,000$ to < 20000	>150 to 300	>180 to 360	16
$\geq 20,000$	>300	>360	24

PEG=polyethylene glycol

1. Standardized rhEPO IV dose (U/week) = $161/113 * (\text{epoetin SC dose (units)} / (\text{frequency}))$ [Beserab, 2002]
2. Conversion of 250 U:1 μg (epoetin IV:darbepoetin alfa) utilized and rounded to the nearest available dose strength [Stern, 2008]
3. Conversion of 1:1.2 μg (darbepoetin alfa:methoxy PEG-epoetin beta) utilized and rounded to the nearest available dose strength [Choi, 2013]
4. Conversion of 208 U:1 μg (epoetin IV: methoxy PEG-epoetin beta)

7.2.1.2. Daprodustat (and Placebo) Titration Doses

The available dose steps of daprodustat are outlined below (gray toned boxes indicate possible starting doses). Dose adjustments will result in the daprodustat dose being increased or decreased by one dose step at a time, as described in the dosing algorithm (Table 7). Participants who are receiving the highest dose of daprodustat (48 mg) and require an additional dose increase, will maintain the same dose. Participants who are receiving the lowest dose of daprodustat (2 mg) and require an additional dose decrease will receive placebo (0 mg) in order to maintain the blind. When a dose interruption is required by the dosing algorithm (Table 7), both daprodustat tablets and saline injections will be interrupted in order to maintain the blind.

Participants who are randomized to daprodustat treatment will also receive inactive treatment for the IV formulation (saline IV). When a dose adjustment is required for these participants, their saline IV dose will be adjusted (in addition to the daprodustat dose) in order to maintain the blind, such that the number of syringes of saline to be administered match the number of vials/syringes required for the new corresponding epoetin alfa dose (Section 7.2.2.2, Table 6).

Table 5 Tablet Combinations to Achieve Prescribed Daprodustat or Placebo Treatment

Dosage Level ¹ (mg)	Total Number of Tablets	Active Treatment for Daprodustat Randomized Participants						Inactive (Placebo) Treatment for Epoetin Alfa Randomized Participants	
		7 mm Placebo	2 mg Dapro	4 mg Dapro	6 mg Dapro	8 mg Dapro	10 mg Dapro	7mm Placebo	9 mm Placebo
0	1	1						1	
2	1		1					1	
4	1			1				1	
8	1					1			1
12	2				2				2
16	2					2			2
20	2						2		2
24	3					3			3
32	4					4			4
48	6					6			6

1. Dose to be administered three-times weekly

7.2.2. Participants Randomized to Epoetin Alfa

Participants who are randomized to the epoetin alfa treatment arm will receive placebo tablets and epoetin alfa IV. A starting dose will be assigned for epoetin alfa as described in Section 7.2.2.1. A starting dose will be assigned for placebo, following the algorithm described for daprodustat in Table 4, and as shown in Table 5. Dose levels will be titrated for both the active and inactive study treatments, and new containers dispensed for each treatment with each change in dose.

7.2.2.1. Epoetin Alfa Starting Dose

The starting dose(s) for participants receiving epoetin alfa are as follows:

- For participants with a Day 1 Hgb ≤ 11.0 g/dL:
 - For participants already on epoetin alfa the starting dose will be the same as their currently scheduled dose, rounded to the nearest available study treatment dose.
 - For participants receiving rhEPO analogs, the starting dose will be an IV epoetin alfa equivalent dose rounded to the nearest available study treatment dose. (Refer to Table 4 for conversion factors to determine equivalent epoetin alfa doses.)
- For participants with a Day 1 Hgb > 11.0 g/dL and ≤ 11.5 g/dL:
 - For participants already on epoetin alfa the starting dose of IV epoetin alfa will be reduced from their current scheduled dose, rounded to the nearest study treatment dose, to the next lower available dose with the aim of maintaining Hgb within the range of 10.0 to 11.0 g/dL.

- For participants receiving rhEPO analogs, the starting dose of IV epoetin alfa will be reduced from their current scheduled rhEPO analog equivalent dose, rounded to the nearest study treatment dose, to the next lower available dose of IV epoetin alfa with the aim of maintaining Hgb within the range of 10.0 to 11.0 g/dL. (Refer to [Table 4](#) for conversion factors to determine equivalent epoetin alfa doses.)

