6.1. Inclusion Criteria

Participants are eligible to be included in the study only if all of the following criteria apply at **screening (Week -4)** and **randomization (Day 1)**, unless otherwise specified:

1. **Age:** Participant must be 18 to 99 years of age inclusive, at the time of signing the informed consent.

Note: Country-specific age requirements for Korea are provided in [Appendix 8](#), Section 12.8.2.

2. **RhEPO or its analogs:** Use of any approved rhEPO or analog for at least 8 weeks prior to the screening visit and continuing during the screening period until randomization (Day 1).
3. **Hemoglobin** concentration (measured by HemoCue) within the following range:

	Hgb Range (inclusive)
Week -4	
 • Hgb 8 to 11.5 g/dL¹ (5 to 7.1 mmol/L). • If Hgb is 11.6 to 11.9 g/dL² (7.2 to 7.4 mmol/L), up to two retests are allowed; the retest value must be between 8 to 11.5 g/dL¹ (5 to 7.1 mmol/L).
Day 1	
 • Hgb 8 to 11 g/dL¹ (5 to 6.8 mmol/L) and receiving at least the minimum rhEPO or analog dose³. • Hgb >11 to 11.5 g/dL¹ (6.8 to 7.1 mmol/L) and receiving greater than the minimum rhEPO or analog dose³.

1. Conversion from g/dL to g/L is 1:10, e.g., Hgb of 8 to 10 g/dL is equivalent to 80 to 100 g/L.
2. The first retest will use the original Week -4 blood sample. If the retest value is >11.5 g/dL, one additional retest can be performed using a new blood sample on the study visit day. The **final** retest value is entered into the IRT system. Retests will be done prior to dialysis.
3. **Minimum rhEPO or analog dose:** Epoetins (including biosimilars): 1500 units (U)/week intravenous (IV) or 1000 U/week subcutaneous (SC); Darbepoetin alfa: 20 µg/4 weeks SC/IV; Methoxy PEG-Epoetin: 30 µg/month SC/IV.

4. **Dialysis:** On hemodialysis (including hemofiltration or hemodiafiltration) >90 days prior to screening and continuing during the screening period.
5. **Frequency of Dialysis:** On hemodialysis (in-center) ≥ 3 times per week.
6. **Sex:** Male and female participants are eligible. A female participant is eligible to participate if she is not pregnant (see [Appendix 4](#)), not breastfeeding, and at least one of the following conditions applies:
 - Not a woman of childbearing potential (WOCBP) as defined in [Appendix 4](#), or

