**Demographics & Baseline Characteristics**

- Darbepoetin alfa only
  - Epoetin only
    - This group contains subjects using any of the following types of epoetin: epoetin alfa, epoetin beta, epoetin lambda, epoetin theta, and epoetin zeta.
  - Methoxy PEG-epoetin beta only
    - This group contains subjects using methoxy PEG-epoetin beta and pegzerepoetin alfa.
  - Multiple
    - This group contains subjects using any combination of the ESA types.
  - Missing
- The dose of ESA will be standardized to obtain a continuous single unit prior ESA dose in terms of epoetin IV U/week for the period from the Week -4 visit to the day before the Randomization date.
  - All prior ESA therapy concomitant medication records from screening will be selected and ordered by start date and end date.
  - The standardization will be carried with the following formula:
  - For subjects taking epoetin IV:
    - Standardized ESA dose (U/week) = epoetin IV dose (U)\*frequency
  - For subjects taking epoetin SC:
    - Standardized ESA dose (U/week) = (161/113)\*epoetin SC dose(units)\*frequency
  - For subjects taking darbepoetin IV or SC:
    - Standardized ESA dose (U/week) = 250\* darbepoetin dose (μg)\*frequency
  - For subjects taking methoxy PEG-epoetin beta:
    - Standardized ESA dose (U/week) = 208\*methoxy PEG-epoetin beta dose (μg)\*frequency

Note: Frequency and Gap Factors defined as follows:

Frequency (from eCRF)	Frequency (for standardization formula)	Gap Factor
One time dose	see below	n/a
Four times per week	4	0.75 day
Three times per week	3	1.33 days
Two times per week	2	2.5 days
Every week	1	6 days
Every 10 days	0.70	9 days
Every 2 weeks	0.50	13 days
Every 3 weeks	0.33	20 days
Every 4 weeks	0.25	27 days
Every 5 weeks	0.20	34 days
Every 6 weeks	0.167	41 days
Every 8 weeks	0.125	55 days

- If the frequency of the record is not 'one time dose', then duration is calculated as follows:

CONFIDENTIAL

204837

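### The comparator starting-dose rule is silent on prior route: read literally, subcutaneous epoetin alfa users start IV epoetin alfa at about 70% of the protocol's own IV equivalent before rounding

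*Protocol*

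**What the plan says.** - **Comparator start (Protocol 7.2.2.1), Day 1 Hgb up to 11.0 g/dL.** "For participants already on epoetin alfa the starting dose will be the same as their currently scheduled dose, rounded to the nearest available" step. The next bullet reads: "For participants receiving rhEPO analogs, the starting dose will be an IV epoetin alfa equivalent dose rounded to the nearest available study treatment dose". Only the analog bullet points to the Table 4 conversion factors.
- **Comparator start, Day 1 Hgb above 11.0 up to 11.5 g/dL.** The same split applies. For epoetin alfa users, "the starting dose of IV epoetin alfa will be reduced from their current scheduled dose, rounded to the nearest study treatment dose"; they then start one step down. Analog users step down from an equivalent dose.
- **Route of study drug (Protocol 7.2.2).** Comparator participants "will receive placebo tablets and epoetin alfa IV".
- **Eligibility (Protocol 6.1, Hgb table footnote 3).** The minimum prior epoetin dose is 1500 U/week IV or 1000 U/week SC, so SC users may enter.
- **Daprodustat start (Protocol 7.2.1.1).** "The starting dose of daprodustat will be assigned based on prior rhEPO or analog dose at randomization, Day 1". Table 4 bands epoetins, biosimilars included, in U/week IV, and footnote 1 standardizes SC doses with the factor 161/113.
- **SAP 14.6.2.1.** "Standardized ESA dose (U/week) = (161/113)\*epoetin SC dose(units)\*frequency". Epoetin alfa is grouped there with the other epoetins.

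Neither document applies the factor to the IV start of someone who enters on SC epoetin alfa.

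**The concern.** The protocol treats SC and IV epoetin units as unequal when it sets eligibility and the tablet start, but the text that sets the IV start for epoetin alfa users does not mention route. One SC epoetin alfa user can therefore carry two prior doses: an IV-standardized one for the tablets and a raw one for the injection. The injection is active only in the comparator arm; in the daprodustat arm it is saline dosed by the same rule. A gap of this kind therefore acts on one arm only, and in a direction that would lower early comparator Hgb.

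It would also not close at once. Table 7 moves the dose one step at a time. Apart from its rules for Hgb below 7.5 g/dL and for rapid falls, an increase needs Hgb below 9.5 g/dL and not rising, or 9.5 to below 10 g/dL at two consecutive visits. The outcomes exposed are those that count from Day 1 or from the starting dose: early Hgb decreases, dose adjustments, transfusions and time to rescue. The rescue criterion in Table 8 counts dose increases above the starting dose.

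**Working it through.** **Inputs.** Factor 161/113 (Table 4 footnote 1; SAP 14.6.2.1). Dose steps from Table 6. Tablet bands from Table 4. The prior dose is taken as the total SC dose per week. (Footnote 1 divides by frequency while the SAP multiplies by it. That is a separate discrepancy and does not enter here.)

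**1. The protocol's own SC/IV pair.** 1000 × 161/113 = 1,425 U/week IV. The nearest Table 6 step is 1500, which is the IV minimum in section 6.1. The eligibility pair is thus consistent with the factor after rounding.

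**2. Gap before rounding.** Same units given IV ÷ IV equivalent = 113/161 = 0.702, a shortfall of 29.8% against the protocol's own equivalence.

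**3. Gap after rounding.** Literal dose = SC dose rounded to Table 6. Converted dose = SC dose × 161/113, rounded to Table 6. Gap = 1 − literal/converted.

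| SC U/week | Literal IV | IV equivalent | Rounded | Steps | Gap |
|---|---|---|---|---|---|
| 1,000 | 1,500 | 1,425 | 1,500 | 0 | 0% |
| 2,000 | 2,000 | 2,850 | 3,000 | 1 | 33% |
| 2,500 (tie) | 2,000 or 3,000 | 3,562 | 4,000 | 2 or 1 | 50% or 25% |
| 4,000 | 4,000 | 5,699 | 6,000 | 2 | 33% |
| 4,500 (tie) | 4,000 or 5,000 | 6,412 | 6,000 | 2 or 1 | 33% or 17% |
| 5,000 | 5,000 | 7,124 | 8,000 | 2 | 38% |
| 7,500 | 8,000 | 10,686 | 10,000 | 1 | 20% |
| 10,000 | 10,000 | 14,248 | 15,000 | 2 | 33% |
| 11,500 | 12,000 | 16,385 | 15,000 | 1 | 20% |
| 15,000 | 15,000 | 21,372 | 21,000 | 2 | 29% |
| 18,000 | 18,000 | 25,646 | 27,000 | 3 | 33% |

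Over SC 2,000 to 15,000 U/week the gap is one or two steps and about 20 to 50%. It reaches 17% only where a tie is rounded up; the protocol gives no tie rule.

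**4. Tablet start.** The IV band edges at 2,000, 10,000 and 20,000 U/week correspond to SC doses of 2,000 × 113/161 = 1,404, 10,000 × 113/161 = 7,019 and 20,000 × 113/161 = 14,037. Conversion therefore changes the daprodustat start only for SC doses of about 1,404 to 2,000, 7,019 to just under 10,000, and 14,037 to just under 20,000 U/week. At 8,000, for example, the band is 12 mg unconverted and 16 mg converted. At 4,000, 5,000 and 10,000 it is the same either way.

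**5. Number affected.** Not given. Assuming 5 to 20% of the 134 comparator participants enter on SC epoetin alfa, that is 0.05 × 134 ≈ 7 to 0.20 × 134 ≈ 27 people. The arm-average starting shortfall would be 0.298 × 0.05 = 1.5% to 0.298 × 0.20 = 6.0%.

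**The case against.** The strongest reply is that this is a gap in wording, not evidence of conduct. Section 7.2.2.1 does not say that SC units are carried over to IV; it leaves route out. Protocol 7.1 leaves examples of switching to the SRM, and dosing runs through the IRT, whose specification is not available. Either may apply footnote 1. This stands: the documents cannot show what anyone received, so a reader should not infer that comparator participants were in fact started low.

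Three further limits also stand.

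- **Product.** A reader might infer that SC users of other epoetins are converted while SC epoetin alfa users are not. Section 7.2.2.1 does not say whether other epoetins count as analogs, and Table 4 puts all epoetins in one column.
- **Tablets.** The Table 4 bands are wide, so the two prior-dose figures give different tablet starts only in the ranges shown.
- **Consequences.** Routine iron under Protocol 7.8.1 depends on ferritin and TSAT, not on Hgb or epoetin dose. The explicit link from low Hgb to IV iron is the optional course in Step 1 of Table 8. A participant who starts one or two steps low is already above the converted start after the three increases that the main rescue criterion requires, which weakens the effect on rescue without removing it.

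None of this supplies the missing route condition. As written, the rule for epoetin alfa users conflicts with the equivalence used elsewhere in the same protocol.

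**Conclusion.** The point holds as an internal inconsistency. Sections 7.2.1.1 and 7.2.2.1, with SAP 14.6.2.1, must be reconciled for participants entering on SC epoetin alfa. On the literal text the comparator start is 70% of the protocol's own IV equivalent before rounding. After rounding it is typically one or two Table 6 steps lower, up to three at some higher doses, and no different at the SC minimum. This takes 161/113 as the protocol's equivalence; it does not say which starting dose is right.

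A reader might go further and infer that the primary non-inferiority comparison is biased towards daprodustat. The documents do not support that as a material effect. Both arms are titrated from Day 1 to Week 28 before the evaluation period, and the share affected is unknown. Early Hgb, dose adjustments, transfusion and rescue are more exposed, but these are secondary or exploratory and carry no multiplicity adjustment. An effect on the principal secondary endpoint, IV iron to Week 52, is possible, but its size is unknown. The matter should be settled; it does not undermine the trial.

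**What to change.** **Protocol and IRT.** Reconcile section 7.2.2.1 with Table 4 footnote 1 and SAP 14.6.2.1, so that one prior-dose figure, on one stated route basis, drives both the tablet and the IV start. The sponsor must decide which passage governs. State whether other epoetins and biosimilars fall under epoetin alfa or under analogs, and check that the SRM examples and the IRT specification agree with the result.

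**SAP.** Flag participants who entered on SC epoetin alfa, using the route recorded with prior medication. Report their number by arm, and repeat the time-to-rescue, early-Hgb and IV iron displays without them as a sensitivity check. This remains possible if dosing can no longer change.

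**Cost.** A clarified sentence or two, one specification check, one derived flag and a few repeat displays on data already collected. The repeat displays will have slightly smaller numbers.
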